9.6.1.2 Phase 3 Cohort

In the Phase 3 Cohort, efficacy endpoints will be collected during the Base and Extension Periods. For the Base Period, the analysis timepoint of interest is Week 12. For the Extension Period, the analysis timepoint of interest is Week 24. Summary statistics will be provided for every planned data collection timepoint described in the SoA (Section 1.3).

Primary Endpoint

The primary estimand for the primary objective used for the Phase 3 Cohort contains 5 attributes:

- The treatment condition of interest is MK-5475 or matching placebo on background stable concomitant PAH-specific therapy, as defined in Section 5.1.
- The population of participants targeted by the clinical question are male/female participants with PAH between the ages of 18 and 75 years (inclusive).
- The variable to address the clinical question is 6MWD at Week 12.
- The following are intercurrent events, along with the approaches to handle them:
 - Death: hypothetical strategy to evaluate 6MWD at Week 12 as though death would not occur.

• Treatment discontinuation: treatment policy strategy seeking to use every participant's actual Week 12 value, regardless of whether they are still taking study medication.

The approach to handling missing data for these intercurrent events is described below.

• The population-level summary is mean change from baseline in 6MWD at Week 12.

For this estimand, the primary approach will use a robust regression method to address the primary hypothesis. Robust regression method will be used because change from baseline in 6MWD is not expected to follow a normal distribution, based on other Phase 3 clinical trials which have used non-parametric methods for analyzing 6MWD [Rubin, L. J., et al 2002] [Rubin, L. J., et al 2015]. The robust regression model will include a term for treatment and WHO-FC (Class II and Class III/IV). Missing 6MWD observations at Week 12 from participants in all treatment groups will be imputed following a PMM. Missing data due to death will be imputed based on the worst outcome among all observed data. Missing data due to treatment discontinuation will be imputed based on the observed 6MWD observations at Week 12 from the placebo group referred as J2R (detailed below). If there are missing Week 12 data for other reasons, J2R will also be used. The randomization seed for imputations will be 5475007.

The difference in change from baseline and the associated 95% CI and *p*-value will be provided (MK-5475 minus placebo). A *p*-value for the comparison of MK-5475 versus placebo <0.025 (one-sided) will be considered statistically significant.

The following steps will be taken to perform the primary analysis, including imputation for missing data. Percent change from baseline in 6MWD at Week 12 is the response variable:

- 1. Define imputation model for different missingness patterns:
 - a. Obtain the worst outcome among all observed data.
 - b. Within the placebo group, for participants with both baseline and Week 12 endpoint, an MMRM model including terms for treatment and WHO-FC (Class II and Class III/IV) will be fit.
- 2. The same procedure in Steps 2 through 6 described in Section 9.6.1.1 will be used for analysis.

Two sensitivity analyses of the estimand for change from baseline in 6MWD will be performed to assess the impact of missing data imputation. Within the same PMM structure in the primary analysis, for missing data due to reasons other than death, 1 analysis will use a tipping point approach and the other analysis will use an approach referred to as washout imputation. The analysis approaches are the same as in the 2 sensitivity analyses described in Section 9.6.1.1 except the missing data due to reasons other than death will be imputed by the MMRM model in the primary analysis.

As a supplemental analysis, the primary analysis will be repeated, excluding participants who participated in the Phase 2 Cohort.

Secondary Endpoint

The primary approach for addressing the mean change from baseline in 6MWD at Week 24 will use the same robust regression method in Section 9.6.1.1. Summary statistics will be provided for the proportion of participants whose WHO-FC is not worse at Week 12 relative to baseline. Table 6 summarizes the analysis strategy for efficacy endpoints in the Phase 3 Cohort.

Endpoint	Туре	Statistical Method	Analysis Population	Missing Data Approach
Primary Endpoint				
Change from baseline in 6MWD at Week 12	P Sen Sen	RR RR RR	FAS FAS FAS	PMM-J2R PMM-Tipping point PMM-Washout
Secondary Endpoints				
Change from baseline in 6MWD at Week 24	Р	RR	FAS	PMM-J2R
Proportion of participants whose WHO functional class does not worsen at Week 12 relative to baseline.	Р	SS	FAS	N/A

Table 6	Analysis Strategy for Primary and Secondary Efficacy Endpoints in the Phase
	3 Cohort

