5.1 Inclusion Criteria

An individual is eligible for inclusion in the study if the individual meets all of the following criteria:

Type of Participant and Disease Characteristics

- 1. Has the following PAH groups, as defined by the Updated Clinical Classification of Pulmonary Hypertension (Nice, 2018) [Simonneau, G., et al 2019]:
 - a. Group 1.1 Idiopathic PAH
 - b. Group 1.2 Heritable PAH
 - c. Group 1.3 Drug and toxin-induced PAH
 - d. Group 1.4 PAH associated with:
 - Connective tissue disease
 - HIV infection
 - Simple repaired congenital systemic-to-pulmonary shunt (atrial septal defect, ventricular septal defect, patent ductus arteriosus) with persistent $PH \ge 1$ year after surgical repair and with no clinically significant residual shunt.
- 2. Has a diagnosis of PAH performed as standard of care, per scientific guidelines, and documented by historical RHC at any time prior to Screening; if participant is postsurgical repair of systemic-to-pulmonary shunt, diagnostic RHC must have been performed at least 1 year after surgery.
- 3. Has an eligibility RHC, meeting all the following criteria:
 - mean pulmonary artery pressure (mPAP) \geq 25 mmHg
 - PVR of \geq 3 Wood units
 - PCWP or LVEDP ≤ 15 mmHg.

For the Phase 2 Cohort, the eligibility RHC should be performed during Screening and will be centrally reviewed. A participant with RHC performed ^{COL} prior to Visit 1/Screening may have the RHC results submitted for central review and, if deemed

adequate, the RHC may count as baseline. In each case, the RHC should be performed after at ^{CCI}.

For the Phase 3 Cohort, an RHC performed ^{CCI} prior to Visit 1/Screening may count for eligibility assessment. An RHC will be performed during Screening if an RHC performed ^{CCI} prior to Visit 1/Screening is not available.

- 4. Has WHO-FC symptoms Class II to IV.
- 5. Has two 6MWD measurements between 150 and 500 meters, 1 at Screening and 1 at Randomization. The relative difference between the 2 measurements (ie, absolute difference/mean) must be ≤15%. If the relative difference between the two 6MWD measurements is >15%, the Randomization 6MWT may be repeated after at least 4 hours. If the relative difference between the 2 Randomization 6MWD measurements is ≤15%, the participant can be randomized and the last 6MWD will be considered the baseline value.
- 6. Has stable concomitant background PAH-specific therapy

with any of the following agents:

- an ERA and/or
- a PDE5i and/or

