9 STATISTICAL ANALYSIS PLAN

This section outlines the statistical analysis strategy and procedures for the study. If, after the study has begun, but prior to any unblinding, changes are made to primary and/or key secondary hypotheses, or the statistical methods related to those hypotheses, the protocol will be amended (consistent with ICH Guideline E-9). Changes to exploratory or other non-confirmatory analyses made after the protocol has been finalized, but prior to final database lock, will be documented in a supplemental SAP (sSAP) and referenced in the Clinical Study Report (CSR) for the study. Post hoc exploratory analyses will be clearly identified in the CSR.

Other planned analyses (ie, those specific to the analysis of PK data and future biomedical research) are beyond the scope of this document.

In this operationally seamless adaptive Phase 2/3 study, all statistical analyses will be separated to address the primary/secondary/exploratory objectives in the Phase 2 Cohort and the Phase 3 Cohort independently. The dose of MK-5475 used in the Phase 3 Cohort will be determined based on the analysis of data collected in the Phase 2 Cohort Base Period.

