9.4.2 Phase 3 Cohort Efficacy Endpoints

Primary Efficacy Endpoint

• Mean change from baseline in 6MWD at Week 12

Secondary Efficacy Endpoint

- Mean change from baseline in 6MWD at Week 24
- Proportion of participants whose WHO-FC is not worse at Week 12 relative to baseline

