9.5.1 Efficacy Analysis Population

The FAS population will serve as the primary population for all efficacy analyses. All randomized participants in the respective cohort who receive at least 1 dose of study treatment will serve as the basis for this population. For PVR and 6MWD, inclusion in the FAS population also requires having a baseline observation. For other efficacy endpoints except TTCW, inclusion in the FAS population requires having at least 1 observation (baseline or post-baseline). Participants will be included in the treatment group to which they are randomized.

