9.6.1.1 Phase 2 Cohort

In the Phase 2 Cohort, efficacy endpoints will be collected during the Base and Extension Periods. For the Base Period, the analysis timepoint of interest is Week 12. For the Extension Period, the analysis timepoint of interest is Week 24. Summary statistics will be provided for every planned data collection timepoint described in the SoA (Section 1.3).

Primary Endpoint

Following the ICH E9 (R1) guidance [European Medicines Agency 2020], The primary estimand for the primary objective used for the Phase 2 Cohort contains 5 attributes:

• The treatment condition of interest is MK-5475 or matching placebo with stable concomitant PAH-specific therapy, as defined in Section 5.1.

- The population of participants targeted by the clinical question are male/female participants with PAH between the ages of 18 and 75 years (inclusive).
- The variable to address the clinical question is PVR at Week 12.
- The following are intercurrent events, along with the approaches to handle them:
 - Death: hypothetical strategy to evaluate PVR at Week 12 as though death would not occur.
 - Treatment discontinuation: treatment policy strategy seeking to use every participant's actual Week 12 value, regardless of whether they are still taking study medication.

The approach to handling missing data for these intercurrent events is described below.

• The population-level summary is mean percent change from baseline in PVR at Week 12.

For this estimand, the primary approach will use a robust regression method to address the primary hypothesis. Robust regression method will be used because percent change from baseline in PVR is not expected to follow a normal distribution, based on other Phase 2 clinical trials which have used non-parametric methods for analyzing PVR [Simonneau, G., et al 2012] [Ghofrani, H. A., et al 2010]. The robust regression model will include terms for treatment and WHO-FC (Class II and Class III/IV). Missing PVR observations at Week 12 from participants in all treatment groups will be imputed following a PMM. Missing data due to death will be imputed as the worst outcome among all observed data. Missing data due to treatment discontinuation will be imputed based on the observed PVR observations at Week 12 from the placebo group referred as J2R (detailed below). If there are missing Week 12 data for other reasons, J2R will also be used. The randomization seed for imputations will be 5475007.

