The difference (MK-5475 minus placebo) in percent change from baseline and the associated 95% CI and *p*-value will be provided. A *p*-value for the comparison of MK-5475 versus placebo <0.025 (one-sided) will be considered statistically significant contingent upon the multiplicity strategy (Section 9.8).

The following steps will be taken to perform the primary analysis, including imputation for missing data. Percent change from baseline in PVR at Week 12 is the response variable:

- 1. Define imputation model for different missingness patterns:
 - a. Obtain the worst outcome among all observed data.
 - b. Within the placebo group, for participants with both baseline and Week 12 data, fit an ANCOVA model including terms for treatment and WHO-FC (Class II and Class III/IV).

- 2. Impute missing data for different missingness patterns:
 - a. Death: for participants (in both treatment groups) who died before Week 12, the worst outcome among all observed data will be used to impute the missing Week 12 values.
 - b. Reasons other than death: For participants (in both treatment groups) missing the response variable, the fitted model in Step 1 will be used to impute the missing values.
- 3. Robust regression based on a Huber-type M estimator [Huber, P. J. 1973] will be performed for the imputed dataset. The model will include terms for treatment and WHO-FC (Class II and Class III/IV).
- 4. Steps 2 and 3 will be repeated 50 times to create 50 complete datasets and 50 sets of parameter estimates.
- 5. The final parameter estimate for the mean percent change will be the average of the 50 parameter estimates for the mean percent change from Step 4.
- 6. Steps 1 through 5 will be repeated 200 times based on bootstrap resampling. The resulting standard error for the mean percent change will be the standard error of the resulting parameter estimates obtained in the 200 bootstrap resampled datasets. The CI and *p*-value will be derived from a normal distribution based on the final parameter estimate and its standard error.

Two sensitivity analyses for percent change from baseline in PVR will be performed to assess the impact of missing data imputation. Within the same PMM structure in the primary analysis, for missing data due to reasons other than death, 1 analysis will use a tipping point approach and the other analysis will use an approach referred to as washout imputation.

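### The primary regressions leave out continuous baseline 6MWD or PVR, although every analysed participant has it

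*Combined protocol and SAP*

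**What the plan says.** Section 9.6.1.1 gives the Phase 2 model for percent change in PVR: "The robust regression model will include terms for treatment and WHO-FC (Class II and Class III/IV". Step 3 of the algorithm there repeats it: "The model will include terms for treatment and WHO-FC (Class II and Class III/IV". Section 9.6.1.2 gives the Phase 3 model for 6MWD: "The robust regression model will include a term for treatment and WHO-FC (Class II and Class III/IV". No section adds a continuous baseline covariate. Baseline 6MWD, and baseline PVR in Phase 2, appear only as subgroup variables (Section 9.10).

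The covariate is complete by definition, because Section 9.5.1 says: "For PVR and 6MWD, inclusion in the FAS population also requires having a baseline observation".

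Two neighbouring passages matter:

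- The Phase 3 response variable is stated in two ways. Section 9.4.2 has "Mean change from baseline in 6MWD at Week 12", and the estimand in 9.6.1.2 and Table 6 agree. The algorithm in 9.6.1.2 has "Percent change from baseline in 6MWD at Week 12 is the response variable".
- The imputation models in Step 1b (an ANCOVA in Phase 2, an MMRM in Phase 3) are fitted within the placebo group, yet list treatment and WHO-FC as their terms.

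**The concern.** If the baseline value predicts the response beyond what two-level WHO-FC explains, the planned estimate has a wider confidence interval than the collected data allow. Chance imbalance in baseline between arms is part of that same variance and not a further harm. Randomisation keeps the planned comparison valid, so neither bias nor Type I error is in question. What is at stake is precision that could be had without more participants or more data.

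The Step 1b wording is a lesser matter. A treatment term cannot be estimated from placebo participants alone; software will drop it and no imputed value changes. But the model names and the short lists of terms leave it unclear whether baseline, and visit in the MMRM, were meant to be included.

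**Working it through.** **Inputs from the documents (Section 9.9.1).** Phase 3: 143 per group, effect 27 m after jump-to-reference dilution, SD 70 m. Phase 2: 41 per group, effect 27 percentage points after dilution, SD 0.4. One-sided alpha is 0.025 in both. The stated SDs are taken as per-participant SDs under the planned model.

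**Reproducing the stated power.** Power = Φ(θ − 1.96), with θ = effect / (SD × √(2/n)).

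- Phase 3: θ = 27 / (70 × √(2/143)) = 3.262, power 90.3% (stated 90%).
- Phase 2: θ = 0.27 / (0.4 × √(2/41)) = 3.056, power 86.4% (stated approximately 86.4%).

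**Assumptions not in the documents.** r is the correlation of baseline with the response; g is the correlation of WHO-FC with baseline, set to 0.5; WHO-FC is taken to act on the response only through baseline.

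**Closed form.** Share of variance removed: R² = r²(1 − g²) / (1 − r²g²). Adjusted power = Φ(θ/√(1 − R²) − 1.96). Equivalent extra participants per arm = n/(1 − R²) − n. For example, at r = 0.3: R² = 0.09 × 0.75 / (1 − 0.0225) = 0.069; Phase 3 power = Φ(3.262/√0.931 − 1.96) = 92.2%; extra n = 143/0.931 − 143 = 10.6.

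| r | Variance removed | Phase 3 power | Extra n per arm of 143 | Phase 2 power | Extra n per arm of 41 |
|---|---|---|---|---|---|
| 0 | 0% | 90.3% | 0 | 86.4% | 0 |
| 0.1 | 0.8% | 90.6% | 1.1 | 86.6% | 0.3 |
| 0.2 | 3.0% | 91.2% | 4.5 | 87.4% | 1.3 |
| 0.3 | 6.9% | 92.2% | 10.6 | 88.6% | 3.0 |
| 0.4 | 12.5% | 93.7% | 20.4 | 90.4% | 5.9 |
| 0.5 | 20.0% | 95.4% | 35.8 | 92.7% | 10.2 |

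Over r = 0.1 to 0.5, g = 0 gives 90.6–96.5% (Phase 3) and 86.7–94.2% (Phase 2); g = 0.6 gives 90.5–94.9% and 86.6–92.0%.

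**Simulation of the change itself.** The closed form ignores dropout and imputation. The simulation used a Huber estimator (tuning constant 1.345) with WHO-FC in both models, baseline added to the regression only, 10% dropout, placebo-based imputation on WHO-FC only, 3 imputations, normal errors, g = 0.5 and 3,000 trials. Power is Φ(θ/√ratio − 1.96), where ratio is the variance with baseline divided by the variance without.

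| r | Ratio, Phase 3 | Power, Phase 3 | Ratio, Phase 2 | Power, Phase 2 |
|---|---|---|---|---|
| 0 | 1.005 | 90.2% | 1.012 | 85.9% |
| 0.1 | 0.993 | 90.5% | 1.003 | 86.3% |
| 0.2 | 0.980 | 90.9% | 0.985 | 86.9% |
| 0.3 | 0.952 | 91.7% | 0.953 | 87.9% |
| 0.5 | 0.832 | 94.7% | 0.853 | 91.1% |

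These are the figures to use if only the regression is changed. A separate Huber simulation with heavier-tailed (t, 5 df) errors and no dropout (143 per group, 600 runs per r) gave ratios of 1.00, 0.95, 0.91, 0.84 and 0.73 at r = 0, 0.2, 0.3, 0.4 and 0.5. The treatment estimate stayed near 27 m with and without baseline.

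**The case against.** The strongest reply is that this is a design choice and not a defect. Both cohorts meet their power targets as planned, and the only stratification factor is already in the model. The size of the gain rests on r and g, which the documents do not supply, and there are reasons to expect a small r. Section 5.1 restricts baseline 6MWD: "Has two 6MWD measurements between 150 and 500 meters, 1 at Screening and 1 at Randomization". Percent change in PVR already divides by baseline. At r = 0.1 to 0.2 the simulated Phase 3 gain is only 0.2 to 0.6 points. The simulation also departs from the plan: normal errors, 3 imputations instead of 50, and no worst-value imputation for deaths. Finally, an amendment is not free, and the blinding rules may close the route.

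Most of this stands as a limit on size. The gain may be negligible, and nothing in the documents shows that r reaches 0.3. The simulation supports the direction and rough scale, not an exact figure. It does not overturn the point: the downside at r = 0 is a variance penalty of about 0.5% (Phase 3) or 1.2% (Phase 2), and Section 9.6.1.2 needs editing in any case to settle its response variable.

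**Conclusion.** The point holds as an improvement that should be made, not as an error. The primary models omit a prognostic candidate that is complete in the analysis set. Changing only the regression, and assuming r between 0.1 and 0.5 with g = 0.5, Phase 3 power moves from 90.3% to between about 90.5% and 94.7%. Phase 2 moves from 86.4% to between about 86.3% (no gain) and 91.1%. Confidence in the size is moderate at best, because r is unknown. The Phase 3 figures hold only for absolute change in 6MWD. The documents do not settle whether Phase 2 is still blinded, so the main value lies in Phase 3.

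**What to change.** - **Phase 3.** Add continuous baseline 6MWD to the robust regression beside treatment and WHO-FC.
- **Phase 2.** Add baseline PVR to the primary regression only if that cohort is still blinded; otherwise report it as a labelled supportive analysis.
- **Same amendment.** Reconcile change with percent change in 6MWD across Sections 9.4.2 and 9.6.1.2 and Table 6. In Step 1b, delete the treatment term and state whether baseline, and visit for the MMRM, are included. Putting baseline in the imputation model too, and in the secondary 6MWD regressions (Phase 2 Week 12, Phase 3 Week 24), would be a useful extension that keeps the models aligned.

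**Cost.** One covariate per primary model, no new data and no change in sample size. It does need a protocol amendment, because Section 9 requires one for changes to the methods behind the primary hypotheses: "If, after the study has begun, but prior to any unblinding, changes are made to primary and/or key secondary hypotheses". Section 9.7 keeps anyone unblinded around the interim analysis out of discussions of statistical methods, and Sections 4.1 and 6.3.3 say that selected sponsor staff will see Phase 2 Base Period results. The amendment should therefore be drafted by staff who have seen neither, with authorship and timing documented. If Phase 2 unblinding is held to close the Section 9 route for Phase 3 as well, prespecify the baseline-adjusted Phase 3 model as supportive.

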In the tipping point approach, missing values due to reasons other than death will be imputed based on the first step in the primary analysis with a positive adjustment Δ added for the MK-5475 group. The inference will be carried out for a range of values of Δ . The smallest value of Δ that renders the significant result into a non-significant result will be the tipping point value, which provides a measure of robustness of the primary result.

In the washout imputation approach, missing values due to reasons other than death in the MK-5475 group will be imputed from a normal distribution with the expected value set to the baseline value in the MK-5475 group and standard deviation computed based on the root mean squared error from the ANCOVA model described in the primary analysis. Missing values in the placebo group will be imputed in the same way as in the primary analysis.

Secondary Endpoint

The primary approach for addressing the mean change from baseline in 6MWD at Week 12 will use the same robust regression method described above for the primary endpoint. Summary statistics will be provided for other selected hemodynamic parameters listed in

Section 9.4.1. Table 5 summarizes the analysis strategy for efficacy endpoints in the Phase 2 Cohort.

Endpoint	Туре	Statistical Method	Analysis Population	Missing Data Approach
Primary Endpoint				
Percent Change from baseline in PVR at Week 12	P Sen Sen	RR RR RR	FAS FAS FAS	PMM-J2R PMM-Tipping point PMM-Washout
Secondary Endpoints				
Change from baseline in 6MWD at Week 12	Р	RR	FAS	PMM-J2R
Change from baseline in selected hemodynamic parameters at Week 12	Р	SS	FAS	N/A

Table 5Analysis Strategy for Primary and Secondary Efficacy Endpoints in the Phase
2 Cohort

6MWD=6-minute walk distance; FAS=full analysis set; J2R=jump-to-reference; N/A=not applicable; P=Primary PMM=pattern mixture model; PVR=pulmonary vascular resistance; RR=robust regression; Sen=Sensitivity; SS=summary statistics.

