Through 12 weeks post-randomization, drop-out is expected to be approximately 10% in each treatment group. However, based on the approach to missing data, all randomized participants per group are expected to be included in the primary analysis and are the basis for sample size and power calculations, accounting for imputation of missing data.

Power and sample size are based on the change from baseline in 6MWD at Week 12. Assuming the true change from baseline in 6MWD at Week 12 is 30 meters for MK-5475 versus 0 meters for placebo, the assumed change from baseline in 6MWD at Week 12 using J2R to impute missing data would be 27 meters for MK-5475 versus 0 meters for placebo. The assumed standard deviation of the difference of change from baseline in 6MWD at Week 12 between each MK-5475 and placebo is 70 meters. Under these assumed change and standard deviation, a sample size of 143/group provides 90% power to demonstrate superiority for each of the MK-5475 treatment comparisons using a one-sided alpha=0.025.

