10.1.4.4 Clinical Adjudication Committee (CAC)

A CAC will evaluate the following events (including events from participants who continue to be followed after discontinuation of double-blinded study intervention) for the purposes of confirming them according to the criteria in Section 8.2.6, as well as evaluating the presence of confounding factors.

TTCW composite endpoint components:

- PAH-related mortality TTCW:
 - 1. PAH-related death
 - 2. PAH-related hospitalization
 - 3. Disease progression as assessed by WHO-FC, 6MWD, and need for additional treatment.
- All-cause mortality TTCW:
 - 1. All-cause death
 - 2. PAH-related hospitalization
 - 3. Disease progression as assessed by WHO-FC, 6MWD, and need for additional treatment

All personnel involved in the adjudication process will remain blinded to study intervention allocation throughout the study.

Specific details regarding endpoint definitions can be found in the CAC Charter.

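### The estimand treats death as if it had not happened while the analysis scores it as the worst outcome, and no analysis as written gives a poor 6MWD to a living participant whose Week 12 test is missing because PAH left them unable to walk

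*Combined protocol and SAP*

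**What the plan says.** Section 9.6.1.2 lists two intercurrent events for the Phase 3 primary estimand. Treatment discontinuation gets a treatment-policy strategy. Death gets this one: "Death: hypothetical strategy to evaluate 6MWD at Week 12 as though death would not occur". The analysis text that follows says: "Missing data due to death will be imputed based on the worst outcome among all observed data". Section 9.6.1.1 pairs the same two rules for PVR in Phase 2, and its Step 2a puts the worst-value rule into the algorithm that Phase 3 reuses.

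There are only two missing-data patterns, death and everything else. The second is imputed in both arms from a model fitted to placebo participants. Section 9.6.1.2 closes the list with: "If there are missing Week 12 data for other reasons, J2R will also be used".

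Two sensitivity analyses, defined for PVR in 9.6.1.1 and carried to 6MWD in 9.6.1.2, vary only the non-death pattern. In the washout analysis, missing MK-5475 values are "imputed from a normal distribution with the expected value set to the baseline value in the MK-5475 group", and missing placebo values stay as in the primary analysis. The tipping-point analysis adds a positive shift to imputed MK-5475 values. Section 9.6.1.2 changes the imputation model but not the sign.

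**The concern.** Under a hypothetical strategy the target is the walk distance participants would have had if nobody died. Under worst-value scoring, death is itself a bad result and enters the comparison as one. These are different treatment effects, so the reported estimate would not answer the question the estimand states, in either cohort.

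The second issue concerns participants who are alive at Week 12 but whose walk test is missing because they were too ill from PAH. The reason for the missing value is informative: on a walking scale, inability to walk is close to a known poor result. The plan instead draws a value from placebo participants who were able to walk. A treatment that prevents such failures gets no credit for it in the primary estimate, and one that causes them is not charged. A prespecified sensitivity analysis would normally show whether this matters; as written, neither of the two does.

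**Working it through.** **1. Death.** Set side by side, the estimand evaluates 6MWD as if death had not occurred, and the estimator assigns the worst observed value because death occurred. No event rate is needed to see that they disagree. The Huber-type estimator then limits the weight of extreme values, so a death counts as a failure, but not at full size.

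**2. The plan's own figure.** Inputs from Section 9.9.1: "Assuming the true change from baseline in 6MWD at Week 12 is 30 meters for MK-5475 versus 0 meters for placebo"; about 10% drop-out per arm; SD 70 m, read as the per-arm SD; 143 per group; one-sided alpha 0.025.

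- J2R dilution: 0.90 × 30 + 0.10 × 0 = 27 m. This matches "using J2R to impute missing data would be 27 meters for MK-5475 versus 0 meters for placebo".
- Standard error: 70 × √(2/143) = 8.28 m.
- Power: Φ(27/8.28 − 1.96) = Φ(1.30) = 90.3%. This matches "a sample size of 143/group provides 90% power to demonstrate superiority for each of the MK-5475 treatment comparisons using a one-sided alpha=0.025".

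The planning calculation therefore places the whole 10% at the placebo mean, with no allowance for worst-scored deaths or for participants unable to walk.

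**3. What the sensitivity analyses can show.** On the arithmetic-mean scale, with 10% missing in the MK-5475 arm:

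- Washout centres missing MK-5475 values on zero change. The planning assumption for placebo is also 0 m, so the expected estimate is again 0.90 × 30 + 0.10 × 0 = 27 m. Nothing is stressed.
- Tipping point: estimate = 27 + 0.10 × Δ. With Δ = +50 m it is 32 m; with Δ = −50 m it is 22 m. For PVR, where lower is better, a positive Δ penalises the drug. For 6MWD, where higher is better, it helps the drug and moves the estimate away from the null.

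**4. Size of the second issue.** Assumptions: 143 per arm; placebo change N(0, 70) and MK-5475 change N(30, 70); 7% missing for other reasons, imputed from placebo; Huber estimator (k = 1.345); model-based standard errors rather than the plan's bootstrap; no WHO-FC term; 3,000 simulated trials per row. Participants too ill to walk receive either J2R (the plan) or the minimum observed change (about −190 m). The rates are assumed.

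| Too ill to walk, placebo / MK-5475 | J2R, as planned | Worst score | Shift | Power, J2R / worst score |
|---|---|---|---|---|
| 3% / 1% | 27.6 m | 30.3 m | +2.7 m | 90% / 93% |
| 5% / 2% | 27.3 m | 31.7 m | +4.4 m | 89% / 94% |
| 2% / 5% | 26.5 m | 24.0 m | −2.5 m | 87% / 75% |
| 2% / 2% | 27.3 m | 27.8 m | +0.5 m | 90% / 89% |

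Under J2R the estimate stays near 27 m whichever way the failures fall. Against a standard error of about 8.6 m, the three imbalanced shifts are about 2.7/8.6 = 0.3, 4.4/8.6 = 0.5 and 2.5/8.6 = 0.3 standard errors. Across equal rates of 1% or 2% the shift is 0.2 to 0.6 m.

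The result depends on the score and the estimator. In a separate set of runs, with failures counted inside the 10% missing and a fixed score of −350 m, 5% on MK-5475 against 2% on placebo gives 24.8 m with the Huber estimator and 16.5 m on the arithmetic mean. With 5% in each arm, the Huber estimate moves from 27.0 to 28.7 m.

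**The case against.** The death conflict has no good defence. The objections concern the second issue, and several of them stand.

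- **It may not arise.** J2R applies only if the value is missing. The visible text does not say whether a participant unable to walk is left missing or entered as 0 m. Section 8.2.2 refers sites to the Study Operations Manual, and Section 8.2.6, which the adjudication section cites for event criteria, is not visible. If 0 m is recorded, it is an observed poor value. This stands, so the point is conditional.
- **The failures are not lost to the trial.** A reader might infer that they are erased. They are not. Section 8.11.5 brings participants who stop treatment during the Base Period back for the full Week 12 visit. Time to clinical worsening, WHO functional class and the safety comparisons also capture deterioration. The leniency is confined to the 6MWD analysis.
- **The tipping-point method is sound in itself.** A reader might infer that it cannot help because it starts from the J2R value. Every delta adjustment starts from a base imputation. In the 2% / 5% scenario, Δ = −100 m on missing MK-5475 values gives about 17 m, below the 24.0 m from worst-scoring. A correctly signed delta therefore covers the harm direction; the defect is the sign.
- **The table compares two estimands.** Neither column is a known truth. Worst-scoring living participants in the primary analysis is a choice of estimand, and the documents do not make it wrong to decline it.
- **Adjudicated progression is a poor trigger.** The committee's definition is "Disease progression as assessed by WHO-FC, 6MWD, and need for additional treatment", so using it to score 6MWD would be partly circular. The committee also confirms clinical-worsening events, not the reason a walk test was missed.

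**Conclusion.** The stated estimand and the analysis disagree on death in both 9.6.1.1 and 9.6.1.2. That is wrong as written and rests on no assumption about event rates.

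For living participants whose Week 12 walk is missing because of PAH-related inability, the plan imputes a placebo-like change, and neither sensitivity analysis as written gives them a poor outcome. In the scenarios tabulated this is worth about 2.5 to 4.5 m under imbalances of 2 to 3 percentage points, and no more than about 0.6 m with equal rates of 1% or 2%. It rests on two things the documents do not settle: that inability is recorded as missing, and how often it occurs. They give only an overall drop-out of about 10%.

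A reader might go further and conclude that the plan favours MK-5475 or conceals harm. The documents do not support that. The direction depends on which arm has more failures, and if the drug prevents them the planned analysis is conservative. Nor do they show that the primary analysis must change beyond agreement on death.

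**What to change.** 1. **Death, both cohorts.** Make the strategy and the scoring agree. The simplest way, which leaves the analysis unchanged, is to name death as a composite-strategy intercurrent event in 9.6.1.1 and 9.6.1.2. Keeping the hypothetical strategy and changing the imputation would also be coherent, but it alters the primary analysis.
2. **Reason not done.** State in 9.6.1.2 how a walk test not done because of illness is recorded and analysed, and capture the reason on the CRF, assigned blind to treatment.
3. **Sensitivity analysis.** Prespecify at least one that gives tests not done because of PAH-related inability to walk the same worst-outcome score as deaths, keeping J2R for administrative loss or refusal. Base the category on the recorded reason, not on adjudicated disease progression.
4. **Tipping point.** Specify a negative delta for MK-5475 on 6MWD. The positive sign remains right for PVR.

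Cost: a wording change, one CRF item and one extra analysis, with slightly more variance in that analysis, which the Huber estimator limits. Section 9 requires a protocol amendment, before unblinding, for changes to the methods tied to the primary hypotheses, so the wording should go in that way.
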